5.3. Lifestyle Considerations

Based on the preliminary results from food-effect cohort in Study INCB 54828-101, no significant food effect was observed. Pemigatinib may be administered with or without food.

Refrain from consumption of red wine, Seville oranges, grapefruit or grapefruit juice (pomelos, exotic citrus fruits, grapefruit hybrids, or fruit juices) for 7 days before the start of study treatment until after the final dose, as this can influence the metabolism of the study drug.

5.4. Screen Failures

Screen failures are defined as participants who consent to participate in the clinical study but are not subsequently entered in the study. Individuals who do not meet the criteria for participation in this study (screen failure) may be rescreened no more than 1 time.

Tests with results that fail eligibility requirements may be repeated once during screening if the investigator believes the result to be in error. Additionally, a participant who fails screening may repeat the screening process 1 time if the investigator believes that there has been a change in eligibility status. Participants who rescreen must reconsent and be assigned a new participant number.

5.5. Replacement of Participants

No participants will be replaced at any time during this study.

6. STUDY TREATMENT

6.1. Study Treatment Administered

Table 9 presents the study treatment information. Starting dose for all participants is 13.5 mg QD.

Table 9: Study Treatment Information

Study treatment name:	Pemigatinib
Dosage formulation:	Tablet
Unit dose strengths/dosage levels:	4.5 mg tablet/4.5 mg, 9 mg, 13.5 mg, and 18 mg
Route of administration:	Oral
Administration instructions:	1-4 tablet(s) taken every morning (unless otherwise directed)
Packaging and labeling:	Pemigatinib will be provided in bottles; each bottle will be labeled as required per country requirement.
Storage:	Room temperature (15-30°C)

6.2. Preparation, Handling, and Accountability

The investigator or designee must confirm appropriate temperature conditions have been maintained during transit for all study treatments received and any discrepancies are reported and resolved before use of the study treatment.

Only participants enrolled in the study may receive study treatment, and only authorized site staff may supply or administer study treatment. All study treatment must be stored in a secure, environmentally controlled, and monitored (manual or automated) area in accordance with the labeled storage conditions with access limited to the investigator and authorized site staff.

The investigator (or designee) is responsible for study treatment accountability, reconciliation, and record maintenance (ie, receipt, reconciliation, and final disposition records). Inventory and accountability records must be maintained and readily available for inspection by the study monitor and are open to inspection at any time by any applicable regulatory authorities. The investigator or designee must maintain records that document:

- Delivery of study drug to the study site.
- Inventory of study drug at the site.
- Participant use of the study drug including pill counts from each supply dispensed.
- Return of study drug to the investigator or designee by participants.

The investigational product must be used only in accordance with the Protocol. Tablets are not to be crushed, dissolved, or broken. The investigator will also maintain records adequately documenting that the participants were provided the specified study drug. These records should include dates, quantities, and any available batch or serial numbers or unique code numbers assigned to the investigational product and study participants.

Completed accountability records will be archived by the site. The investigator or designee will be expected to collect and retain all used, unused, and partially used containers of study drug until verified by the study monitor (unless otherwise agreed to by the sponsor). At the conclusion of the study, the investigator or designee will oversee shipment of any remaining study drug back to the sponsor or its designee for destruction according to institutional standard operating procedures. If local procedures mandate on-site destruction of investigational supply, the site should (where local procedures allow) maintain the investigational supply until the study monitor inspects the accountability records in order to evaluate compliance and accuracy of accountability by the investigative site. At sites where the study drug is destroyed before monitor inspection, the monitors rely on documentation of destruction per the site SOP.

Instructions for participants regarding the handling of the study drug are in [Appendix B](#).

6.3. Measures to Minimize Bias: Randomization and Blinding

Not applicable. This is an open-label, non-randomized study.

6.4. Study Treatment Compliance

Compliance with all study-related treatments and assessments should be emphasized to the participant by the site personnel and appropriate steps should be taken to optimize compliance during the study.

Compliance with pemigatinib will be calculated by the sponsor based on the drug accountability documented by the site staff and monitored by the sponsor/designee (tablet counts). Participants will be instructed to bring all study drugs with them to the study visits in order for site personnel to conduct tablet counts to assess study drug accountability. The drug accountability documentation will be used by the sponsor to calculate treatment compliance.

6.5. Dose Modifications

Individual decision regarding dose modifications of pemigatinib should be made using clinical judgement and in consultation with the sponsor's medical monitor, taking into account relatedness of the AE to the study treatment and the participant's underlying condition. Adverse events that have a clear alternative explanation or transient (≤ 72 hours) abnormal laboratory values without associated clinically significant signs or symptoms, may be exempt from dose-reduction rules.

6.5.1. Criteria and Procedures for Dose Interruptions and Adjustments of Study Drug

Safety concerns should be discussed with the sponsor immediately upon occurrence or awareness to determine if the participant should continue or discontinue study treatment.

Treatment with pemigatinib may be delayed up to 2 weeks (14 days) to allow for resolution of toxicity. Participants may resume treatment if no medical condition or other circumstance exists that, in the opinion of the investigator, would make the participant unsuitable for further participation in the study. The treating investigator should contact the sponsor to discuss the case of any participant whose treatment has been delayed for more than 14 days before restarting treatment with pemigatinib. Refer to [Table 10](#) for guidelines.

Table 10: Guidelines for Interruption and Restarting of Study Drug

ADVERSE EVENT	ACTION TAKEN
Chemistry	

 AST and/or ALT is $> 5.0 \times$ ULN. Note: In participants with liver metastasis-related elevations at baseline, contact sponsor to discuss clinical management and possible dose reductions. 	
Step 1: Interrupt pemigatinib up to 2 weeks (14 days) until the toxicity has resolved to \leq Grade 1 except by approval of the medical monitor.
 
Step 2: Restart pemigatinib at same dose. If assessed as related to pemigatinib, restart pemigatinib at next lower dose; monitor as clinically indicated.

Other toxicities	

 Any Grade 1 or Grade 2 toxicity. 	Continue pemigatinib treatment and treat the toxicity; monitor as clinically indicated.

 Any Grade 3 toxicity, if clinically significant and not manageable by supportive care. 	
Step 1: Interrupt pemigatinib up to 2 weeks (14 days), until toxicity resolves to \leq Grade 1.
 
Step 2: Restart pemigatinib at same dose. If assessed as related to pemigatinib, restart pemigatinib at next lower dose; monitor as clinically indicated.

 Any recurrent Grade 3 toxicity after 2 dose reductions. 	Discontinue pemigatinib administration and follow-up per Protocol (exceptions require approval of sponsor).

 Any other Grade 4 toxicity. 	Discontinue pemigatinib administration and follow-up per Protocol.

The sponsor recommends a maximum of 2 level dose reductions: participants treated at 13.5 mg can decrease to 9 mg, and if additional dose reduction is required, participants can decrease to 4.5 mg. Dose reductions below 4.5 mg are not allowed. The frequency of dosing (ie, QD) as well as the schedule (ie, continuous dosing) remain the same.

For participants who are up-titrated from 13.5 mg to 18 mg, a maximum of 2 dose level reductions is also recommended. The 18-mg dose can be decreased to 13.5 mg, and if additional dose reduction is required, participants can decrease to 9 mg. Dose reductions below 9 mg are not allowed.

6.5.2. Management of Hyperphosphatemia

Hyperphosphatemia is an expected on-target pharmacologic effect of FGFR inhibition. Hyperphosphatemia should be managed with diet modifications, phosphate binders and diuretics, or a dose reduction per the recommendations in [Table 11](#).

The use of diet modifications alone include food exchanges from high-phosphate foods to low-phosphate foods and can be implemented once serum phosphate levels are above the ULN but do not exceed 7.0 mg/dL. Diet modification should continue with the inclusion of phosphate binders once serum phosphate levels exceed 7.0 mg/dL. An example of a phosphate binder is sevelamer HCl (eg, Renegel®, Renvela®). Administration of phosphate binders should be 3 times per day (eg, with each meal) to reduce absorption of phosphate. Doses and frequency of doses should be based on the participant's tolerance for the binder and the control of serum

phosphate. If binders are used to manage hyperphosphatemia during treatment, it is recommended to stop binders at the same time pemigatinib is stopped to reduce risk of hypophosphatemia.

For grading of hyperphosphatemia, please note that [CTCAE v5.0](#) now has a category for hyperphosphatemia.

Table 11: Recommended Approach for Hyperphosphatemia Management

Serum Phosphate Level	Supportive Care	Guidance for Interruption/Discontinuation of Pemigatinib	Guidance for Restarting Pemigatinib
> 5.5 mg/dL and \leq 7 mg/dL	Initiate a low-phosphate diet	No action.	Not applicable.
> 7 mg/dL and \leq 10 mg/dL	Initiate/continue a low-phosphate diet and initiate phosphate binding therapy. Monitor serum phosphate approximately twice a week and adjust the dose of binders as needed; continue to monitor serum phosphate at least twice a week until return to \leq 7 mg/dL.	If serum phosphate level continues to be > 7 mg/dL and ≤ 10 mg/dL with concomitant phosphate-binding therapy for 2 weeks, or if there is recurrence of serum phosphate level in this range, interrupt pemigatinib for up to 2 weeks	Restart at the same dose when serum phosphate is < 7 mg/dL. If serum phosphate level recurs at > 7 mg/dL, restart pemigatinib with dose reduction.
> 10 mg/dL	Continue to maintain a low-phosphate diet, adjust phosphate-binding therapy, and start/continue phosphaturic agent. Continue to monitor serum phosphate approximately twice a week until return to \leq 7 mg/dL.	If serum phosphate level is > 10 mg/dL for 1 week following phosphate-binding therapy and low-phosphate diet, interrupt pemigatinib. If there is recurrence of serum phosphate level in this range following 2 dose reductions, permanently discontinue pemigatinib.	Restart pemigatinib at reduced dose with phosphate binders when serum phosphate is < 7 mg/dL.

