6.5.4. Criteria for Permanent Discontinuation of Study Drug

The occurrence of unacceptable toxicity not caused by the underlying disease will require that the study drug be permanently discontinued. Unacceptable toxicity is defined as follows:

- Occurrence of an AE that is related to study drug that, in the judgment of the investigator or the sponsor's medical monitor, compromises the participant's ability to continue study-specific procedures or is considered to not be in the participant's best interest.
- An AE requiring more than 2 dose reductions.
- Persistent AE requiring a delay of therapy for more than 2 weeks (14 days) unless a greater delay has been approved by the sponsor.
- Increase in QT/QTc to > 500 milliseconds or to > 60 milliseconds over baseline. In case of a QTc > 500 milliseconds, the participant must be hospitalized and continuous ECG monitoring must be set up until the measure of the QTc interval decreases below 500 milliseconds and is acceptable in the opinion of the local cardiologist.

See Section [7](#) for discontinuation procedures.

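### Section 6.5.2 recommends stopping phosphate binders when pemigatinib is stopped, without excepting stops made because phosphate is high, where Table 11 calls for binder adjustment

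*Protocol*

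**What the plan says.** Section 6.5.2 of the Protocol introduces the topic by pointing to Table 11: "Hyperphosphatemia should be managed with diet modifications, phosphate binders and diuretics, or a dose reduction per the recommendations in" that table. The running text then adds, for participants who have been given binders during treatment, that "it is recommended to stop binders at the same time pemigatinib is stopped to reduce risk of hypophosphatemia". The sentence names no phosphate level and no reason for stopping. It also does not define a stop.

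Table 11 assigns supportive care by serum phosphate level.

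- **Above 7 and up to 10 mg/dL.** Binders are started, with the instruction "Monitor serum phosphate approximately twice a week and adjust the dose of binders as needed". Pemigatinib is interrupted for up to 2 weeks if the level stays in this range "with concomitant phosphate-binding therapy for 2 weeks, or if there is recurrence of serum phosphate level in this range".
- **Above 10 mg/dL.** The supportive care is "Continue to maintain a low-phosphate diet, adjust phosphate-binding therapy, and start/continue phosphaturic agent". Pemigatinib is interrupted if the level is above 10 mg/dL for 1 week after binders and diet, and permanently discontinued if it recurs in this range after 2 dose reductions. The restart rule is "Restart pemigatinib at reduced dose with phosphate binders when serum phosphate is < 7 mg/dL".

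Section 6.5.4 lists among the criteria for permanent discontinuation: "Persistent AE requiring a delay of therapy for more than 2 weeks (14 days) unless a greater delay has been approved by the sponsor".

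**The concern.** The stated reason for ending binders together with pemigatinib is the risk of hypophosphatemia. That reason does not address a stop made because phosphate is too high. In each phosphate-driven stop in Table 11 the level is above 7 or above 10 mg/dL when the rule is triggered, and the same row asks the site to adjust binders. On the day of such a stop a site can find both instructions applying to one participant, with nothing to say which governs.

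Participant safety is at stake, and so is uniform handling of the toxicity that was most frequent in the earlier study. If interruptions are covered by the sentence, there is also a consequence for conduct. Restart depends on phosphate falling below 7 mg/dL, and Section 6.5.4 limits a delay to 14 days unless the sponsor approves more. Differences between sites in binder handling could then change time to restart and exposure.

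**Working it through.** The protocol states no figure on this point, so the check sets the passages side by side under each possible meaning of *stopped*.

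**Step 1. The phosphate-driven stops in Table 11.**

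| Stop | Phosphate at the trigger | Action on pemigatinib | Binder instruction in the same row |
|---|---|---|---|
| A | > 7 to ≤ 10 mg/dL, persisting 2 weeks on binders or recurring | Interrupt | Adjust dose as needed |
| B | > 10 mg/dL for 1 week after binders and diet | Interrupt | Adjust; start or continue a phosphaturic agent |
| C | Recurrence > 10 mg/dL after 2 dose reductions | Permanently discontinue | Adjust; start or continue a phosphaturic agent |

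**Step 2. A stop includes an interruption.** The sentence in 6.5.2 then covers A, B and C. It says to end binders in each, while the row says to adjust them. The conflict is with both rows.

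**Step 3. A stop means permanent discontinuation only.** A and B fall away. C remains: the sentence says to end binders, and the row that triggers the discontinuation says to adjust them. The conflict is with the row above 10 mg/dL.

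**Step 4. Does anything rank one instruction over the other?** The sentence is worded as a recommendation, but Table 11 is likewise titled as a recommended approach. The opening reference to Table 11 is general, and the later sentence is the only one that says when binders end. The restart rule above 10 mg/dL requires binders at restart but does not say whether they ran through the interruption or were resumed. No ranking follows.

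**Step 5. What runs until phosphate is back to 7 mg/dL or below?** In the middle row the clause is "continue to monitor serum phosphate at least twice a week until return to" that level, and the row above 10 mg/dL is built the same way. In both, the end point belongs to monitoring. Binder adjustment has no stated end point.

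**Step 6. How many participants?** Table 6 reports hyperphosphatemia as an adverse event in 14 of 16 participants on 13.5 mg continuous dosing (14/16 = 87.5%). Section 2.3.1 describes that event as phosphate above 5.5 mg/dL. From above 5.5 to 7 mg/dL Table 11 calls for diet and no action on pemigatinib, so this rate does not count the people who would meet the conflict. The shares above 7 and above 10 mg/dL are not given.

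For discontinuation there is a loose bound. Section 2.3.1 names the adverse events that led to discontinuation in more than 1 of the 106 monotherapy participants, and hyperphosphatemia is not among them. It therefore accounted for at most 1 of 106: 1/106 = 0.9%, and 50 × 1/106 = 0.5 of 50 participants. If that one possible case fell among the 16 on 13.5 mg continuous, the bound is 1/16 = 6.3%, and 50 × 1/16 = 3.1 of 50. Both figures assume discontinuation rules similar to this trial's, which the protocol does not show.

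**The case against.** The strongest reply is that this is loose wording that a careful site would read correctly. Table 11 separates interrupting from permanently discontinuing, while the sentence uses neither term and speaks of binders used during treatment, so it can naturally mean the end of treatment. On that reading the two interruption cases are not in conflict, and Table 11 never says outright that binders continue through an interruption. The remaining case, recurrence above 10 mg/dL after 2 dose reductions, is likely to be rare. Section 6.5.2 also ties binder dosing to control of serum phosphate, and Section 6.5 places dose-modification decisions under clinical judgement with the medical monitor. Hypophosphatemia, the stated reason for the sentence, is a real risk: Table 6 shows it in 4 of 16 (25.0%) at 13.5 mg continuous.

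Much of this stands. For interruptions the fault is an ambiguity that becomes a contradiction on one natural reading. The consequences for time to restart belong to that reading alone, since there is no restart after permanent discontinuation. The reply does not remove the conflict above 10 mg/dL, and neither clinical judgement nor the general reference to Table 11 says which instruction governs binders when phosphate is the reason for the stop.

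A reader might infer more than the document supports:

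- That Table 11 orders binder adjustment until phosphate is 7 mg/dL or below. That end point is attached to monitoring.
- That binders would be withdrawn at the peak. The document shows only a level above a trigger.
- That any delay beyond 14 days ends treatment. Section 6.5.4 allows a longer delay with sponsor approval.
- That most participants are affected because 87.5% had hyperphosphatemia. That rate counts levels for which pemigatinib is not held.
- That the primary analysis is damaged. Sections 10.2 and 10.4.1 keep every dosed participant in the ORR denominator, and Sections 8.2.1 and 8.8.2 continue imaging after discontinuation for reasons other than progression.

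**Conclusion.** The point holds as an unreconciled safety instruction. Read to include interruptions, the binder sentence conflicts with both upper rows of Table 11. Read as permanent discontinuation only, it conflicts with the row above 10 mg/dL. No reading considered leaves the section fully consistent.

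The number of participants affected cannot be derived from the protocol. On the narrow reading it is probably small, subject to the assumption about discontinuation rules made above; on the broad reading it is unknown. The weight rests on participant safety and consistent management across sites. The sample size, the ORR test and the posterior-probability rules for tumor subtypes are untouched. No judgement is made here on which binder instruction is clinically right.

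**What to change.** Reconcile the 6.5.2 sentence with Table 11. State which kind of stop the sentence covers: interruption, permanent discontinuation or both. State also which instruction governs binders when pemigatinib is interrupted or discontinued because of phosphate. This can be done by qualifying the sentence, by a footnote to Table 11, or by changing the table to match the sentence. The sponsor decides the clinical rule, and one instruction must remain.

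The cost is one sentence or footnote in a protocol amendment, with notice to sites. It needs no new assessments and no change to the analysis.

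### Table 11 makes recurrence at >7 to 10 mg/dL a trigger to interrupt pemigatinib, but not recurrence above 10 mg/dL before 2 dose reductions, so the higher band may interrupt 0 to 7 days later

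*Protocol*

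**What the plan says.** Section 6.5.2 sends sites to Table 11, whose rows are bands of serum phosphate.

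- **>7 to 10 mg/dL, interruption.** Pemigatinib is interrupted for up to 2 weeks if the level stays in the band for 2 weeks on binders, "or if there is recurrence of serum phosphate level in this range". The second condition carries no waiting period.
- **>7 to 10 mg/dL, restart.** "Restart at the same dose when serum phosphate is < 7 mg/dL". Then: "If serum phosphate level recurs at > 7 mg/dL, restart pemigatinib with dose reduction".
- **>10 mg/dL, supportive care.** Diet is maintained and treatment is stepped up: "adjust phosphate-binding therapy, and start/continue phosphaturic agent".
- **>10 mg/dL, interruption.** The one trigger is "If serum phosphate level is > 10 mg/dL for 1 week following phosphate-binding therapy and low-phosphate diet". The only mention of recurrence is "If there is recurrence of serum phosphate level in this range following 2 dose reductions", and the action there is permanent discontinuation.
- **>10 mg/dL, restart.** "Restart pemigatinib at reduced dose with phosphate binders when serum phosphate is < 7 mg/dL".

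The text above the table adds that, when binders have been used, "it is recommended to stop binders at the same time pemigatinib is stopped to reduce risk of hypophosphatemia".

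The table is titled as a recommended approach. Section 6.5 places individual dose decisions under clinical judgement in consultation with the medical monitor. Section 6.5.1 asks that safety concerns be raised with the sponsor immediately, and its Table 10 interrupts for Grade 3 toxicity that is clinically significant and cannot be managed by supportive care.

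**The concern.** A dose-interruption table should not be slower to act at the more severe level. Here that can happen for one kind of event: phosphate that recurs above 10 mg/dL before 2 dose reductions have been made. Two paths lead there: a rise above 10 mg/dL after a same-dose restart under the >7 to 10 row, or after a first reduced-dose restart under the >10 row.

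On a literal reading, a participant whose phosphate recurs at 9.5 mg/dL is interrupted, while one whose phosphate recurs at 10.5 mg/dL may stay on drug for up to a further week. Hyperphosphatemia is the expected on-target effect, so sites will use this table in practice. What is at stake is participant safety and uniform handling across sites. No effect on the response-rate analysis has been shown.

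**Working it through.** The protocol gives no figure for this point, so the check sets the two rows side by side and then bounds the delay.

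**Step 1: triggers compared.** All entries come from the interruption column of Table 11.

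| Situation | >7 to 10 mg/dL | >10 mg/dL | Which acts sooner or harder |
|---|---|---|---|
| Persistence (first episode) | 2 weeks on binders | 1 week following binders and diet | Higher band |
| Recurrence after 0 or 1 dose reduction | Interrupt, no wait stated | 1-week rule only | Lower band may |
| Recurrence after 2 dose reductions | Interrupt | Permanently discontinue | Higher band |

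The order is as expected in the first and third lines and can reverse only in the second.

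**Step 2: does another rule cover the second line?**

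- The lower row's recurrence trigger is confined to its own range, which ends at 10 mg/dL, so it does not literally reach 10.5 mg/dL.
- The restart sentence "If serum phosphate level recurs at > 7 mg/dL, restart pemigatinib with dose reduction" has no upper limit. A restart presupposes an interruption, so it hints that one was meant, but it sets the dose at restart and not the time of stopping.
- Sections 6.5 and 6.5.1 permit earlier interruption but do not state it for this event. The Grade 3 rule in Table 10 has two conditions that an asymptomatic, treatable rise may not meet.
- Section 6.5.4 concerns permanent discontinuation.

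**Step 3: size of the delay.** The lower band's wait at recurrence is 0 days. The higher band's wait depends on when its week starts, which the cell leaves open.

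- *Reading A, week runs from the recurrence:* 7 − 0 = 7 days. At about two phosphate measurements a week, that is about 2 further measurements.
- *Reading B, week runs from the start of binders and diet:* with d days already on both at recurrence, the delay is max(0, 7 − d).
  - d = 0: 7 − 0 = 7 days
  - d = 3: 7 − 3 = 4 days
  - d = 7 or more: 0 days

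Over both readings the range is 0 to 7 days.

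**Step 4: is a low d plausible?** Possibly. If the advice to stop binders together with pemigatinib applies to an interruption (an assumption), binder treatment would begin again around the recurrence. The same-dose restart text of the lower row does not mention binders. After a restart under the >10 row, binders are required, so d is then the time since that restart or longer.

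**Step 5: how many participants?** Table 6 reports hyperphosphatemia as an adverse event in 14 of 16 participants on 13.5 mg continuous dosing (14/16 = 87.5%). It does not say how many exceeded 10 mg/dL or recurred, so the number affected cannot be derived.

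**The case against.** The strongest reply is that nothing is missing and nothing forces a site to keep dosing. The 1-week rule is not limited to a first episode or to a dose level, so it applies to a recurrence above 10 mg/dL. The supportive-care cell of that row presumes that diet and binders are already in place, so under Reading B the delay is often short or nil. The table is guidance, and a site can interrupt the same day on clinical judgement and after sponsor contact. The row is stricter in every other respect: a shorter persistence period, a phosphaturic agent, a reduced dose at every restart, and permanent discontinuation after 2 reductions. A week for intensified treatment to work could also be a deliberate choice.

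Most of this stands, and it rules out stronger readings that a reader might infer:

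- *That recurrence above 10 mg/dL before 2 reductions has no rule.* It has the 1-week rule.
- *That the higher band always waits a full week while the lower band stops at once.* The lower row has no waiting period but does not say at once, and the delay in the higher row can be zero.
- *That the >10 mg/dL row is the laxer one overall.* Only the interruption timing at recurrence can be out of order.
- *That participants must be kept on drug for the week.* The protocol leaves room to stop earlier.

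Two parts of the reply do not remove the point. The protocol does not give the phosphaturic-agent rationale, and that rationale would not explain why the order reverses for recurrence but not for persistence. Permission to act earlier is also not a stated rule, so two sites following the same table could act differently.

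**Conclusion.** The point holds as a low-severity safety inconsistency in recommended guidance. For recurrence after 0 or 1 dose reduction, the only stated interruption trigger above 10 mg/dL is the 1-week rule, while recurrence at >7 to 10 mg/dL triggers interruption by itself. The literal consequence is an interruption 0 to 7 days later in the higher band.

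The upper end needs either a week counted from the recurrence or little prior time on binders and diet. The latter rests partly on reading the advice to stop binders as applying to interruptions. The pattern of the other two comparisons, together with the open-ended restart text, suggests a drafting gap and not an intended difference. No harm has been quantified.

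**What to change.** In the >10 mg/dL interruption cell, after the 1-week condition and before the instruction to interrupt, add: "or if there is recurrence of serum phosphate level in this range" before 2 dose reductions (including a rise above 10 mg/dL after an interruption under the >7 to 10 mg/dL row). Keep the reduced-dose restart with binders, and keep permanent discontinuation for recurrence after 2 dose reductions. Optionally, limit the recurrence sentence in the restart cell of the >7 to 10 row to that row's own range.

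The cost is one clause in one table cell. It changes a dose-interruption criterion, so a site memo alone is not enough: Section 11.1 requires IRB/IEC approval of a protocol amendment before it is implemented. A few more short interruptions are possible. No extra tests are needed, because both rows already ask for phosphate monitoring about twice a week.
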